Harp's Pharmacy has a successful medication therapy management (MTM) program where pharmacists are provided time for patient-centered activities for patients with diabetes (DM), hypertension (HTN), the 2 leading causes for CKD, and heart failure (HF), the leading cause of death in CKD. Thirty six percent of patients with DM will develop CKD and hypertension can be both a cause and an effect of CKD (5). In this project they will use their MTM infrastructure to add CKD to their program in select pharmacies in the delta. The CKD tools build on and support actions that improve the underlying conditions that are already being addressed. The "CKD: What Your Need to Know" tools will be used with patients with known CKD or 2 of the 3 conditions covered by MTM and randomized into 1 of 3 education arms that offer various levels of support or a control arm.

Using non-nephrology clinicians to expand access to education earlier in their disease progress is essential. This project will inform how various levels of support provided by pharmacists and their staff using nephrology developed tools can effect patient choice allowing comparisons of support time and outcomes. Empowering patients to be proactive partners in their health care, through education and accountability, by choosing both their RRT and performance goals to protect their kidneys is key to improving outcomes. Demonstrating that non-nephrology clinicians can effectively educate and support these patients will provide models that other clinicians can use.

Minorities, especially in rural areas, are less likely to receive most kinds of care including evidence-based practices, home dialysis or transplantation (4,5). Developing patient-centered approaches to care such as this project can reduce disparities.

One-on-one outreach to educate and motivate patients and seek their feedback can strengthen commitment and adherence to medical regimens. Learning what to expect can promote self-management behaviors.

The AR Department of Health (ADH) Southeast (SE) region covers most of the Delta and was selected because it has the poorest outcomes for patients starting RRT. In 2017, new patients were predominately black (61%), less than half had seen a nephrologist prior to starting RRT, only 1.3% had seen a dietitian, most (92.3%) started hemodialysis using a catheter and 2.1% started on home peritoneal dialysis. Only 2.1% had no insurance (9). This data can be tracked annually to track impact.

The tools being used were developed by a multidisciplinary team of nephrology experts which are limited in the delta. Courses including train the trainer classes for pharmacies and 10 points of Care for CKD for clinicians will be conducted. Collaboration with local providers can both educate and promote community engagement.

Harp pharmacists expressed randomization concerns. They report that many of their MTM subjects have multiple family members or friends enrolled in the study. This could confound randomization into various arms since these subjects are highly likely to compare and contrast the details of their intervention. It was decided that a cluster randomization schedule would be utilized with each cluster self-selecting a leader that would be enrolled in the study and be responsible for education of the other cluster

members. All cluster members will undergo the same testing.

Specific Aims

The primary aim is to assess the effectiveness of pharmacists and their staff to educate CKD and high risk patients evaluating effectiveness through patient choice of RRT in each arm (e.g. home dialysis choice rate). Secondary aims include 1) Identify actions patients are willing to take to protect their kidney function using the CKD Action Plan that contains 10 performance goals based on international CKD guidelines that can slow CKD progression 2). Describe outcomes and methods used by peer leaders to educate cluster members using the same goals. 4) Compare costs (based on pharmacist and pharmacy associate time) with outcomes in each arm.

Study Design and Procedures

This study is a randomized control pilot study using non-nephrology clinicians to educate patients who are at high risk for CKD how to protect their kidneys and be ready for RRT if and when needed by utilizing nephrology developed educational tools.

Harp's pharmacists will screen patients in their MTM program and enroll them in familial or peer clusters consisting of 1 or more subjects and randomize them into 1 of the 4 study arms using a site specific randomization schedule. Each arm will receive pre and post testing and health literacy evaluation. Two education arms will use the 139 page CKD: What You Need to Know workbook including the CKD Action Plan as self-study tools and follow-up during regular MTM appointment. The 3 arms include 2 education arms and a control arm with various levels of intervention: Arm 1) case management model including pharmacist initiated discussion of workbook content and action plan reinforcement, Arm 2) brief introduction of the workbook and action plan reinforcement, Arm and Arm 3) the control group will receive a list of web-based CKD sites and a copy of the action plan with no additional intervention. Patient initiated CKD discussions will be tracked by both the pharmacist and staff by topic and time spent. Time spent by the pharmacist and staff will be calculated along with outcomes and compared in each group. Data collected upon enrollment will include year of birth, race, gender, county of residence, history of CKD, diabetes, hypertension and/or heart failure, patient reported blood pressure, AIC, eGFR and hemoglobin, smoking history, renal transplant history and if is under the care of or has been seen by a nephrologist in the past.

The CKD: What You Need to Know Workbook is 139 pages and includes:

- An Introduction
- 8 Chapters plus resources:
 1. Kidneys and Chronic Kidney Disease (CKD)
 2. Protecting Your kidneys and Slowing CKD Progression
 3. Your Choices for Dialysis and Transplantation
 4. Lab Results: What they mean & What you can control
 5. Chronic Kidney Disease & Eating Habits

6. Chronic Kidney Disease & Meds
7. Learning to Cope with Kidney Disease
8. Paying for Your CKD Treatment
9. CKD Action Plan
10. Web-based Resources
11. Kidney Talk: What do these words mean?
12. Resources

Each section ends with “Frequently Asked Questions”, “Test Your Knowledge” and has space for notes. Patient testimonies are found at the back of 6 chapters.

The workbook went through health literacy editing with a goal of a 5th grade reading level. The chapters ranged from 3rd to 7th grade levels. It was felt that it was important for subjects to learn or at least be exposed to words that were kidney related and frequently used by their health care providers. So the first time each of these words were used in the workbook they were red and the definition was in the kidney talk section on that page. Then the first time the word appeared in subsequent chapters the word was in red but no definition was on that page.

Subjects will be randomized into 1 of 2 education arms that offer various levels of support or a control arm using a site specific computer generated randomization schedule. Presumed monthly visits.

Study Arm	Handouts	Visit 1*	Visit 2	Visit 3	End of Study June 2022
Testing		Pre-test		Post-Test	Evaluation
1: Case Study Model	Workbook Action Plan (V1) Label reading Exercise (V2)	Pharmacist initiated review of workbook and assist with Action Plan goal selection	Action Plan Reinforcement. Discuss Chapters 1-4. Provide “Label Reading Exercise”	Action Plan Reinforcement. Discuss Chapters 5-8 and resources. Review results of Label exercise	Open conversations from each party for all arms after evaluation
2: Minimal Instruction	Workbook Action Plan	Briefly explain handouts with focus on Action Plan.(5-10 minutes)	Action Plan Reinforcement. Answer patient’s questions.	Action Plan Reinforcement. Answer patient’s questions.	As Above
3: Control	Resource List Action Plan	Answer patient’s questions.	Answer patient’s questions.	Answer patient’s questions.	As Above

*On first visit, education arms subjects will be asked to read 1 chapter of the workbook weekly. All subjects will receive a CKD Action Plan and be asked to set individual goals.

Secondary outcome data collected at each visit include both self-reported and/or

Title: Pragmatic Approach to Chronic Kidney Disease Education in the Delta V.6

PI: [name]

pharmacist or physician confirmed blood pressure and AIC, eGFR, hemoglobin. Patient and/or pharmacist initiated CKD conversation and topics including CKD action plan goal progress. The action plan has 1 knowledge goal related to CKD cause, eGFR and trend and 10 performance goals based on international guidelines and best practices including AIC goal of 7 or less, blood pressure goal of less than 140/90, exercise goal of 30 minutes 5 times a week, medications that may need to be avoided (ex: ibuprofen) or may need to be taken (ex: Statin) if you have CKD and DM or over 50 years old), smoking cessation, kidney friendly diet (may need to modify salt, phosphorus and/or protein intake and be edema free [may require monitoring and adjust salt and water intake], home monitoring of blood pressure, blood sugar and weight, weight management and anemia (goal hemoglobin above 10g/dL)

Study Population

High Risk Subjects will be identified from the Harps MTM program or others having multiple known medical problems (CKD, HTN, DM or heart disease). Know Your Kidney Number Posters which will be available statewide by the time the study starts will be posted in the pharmacy. Even though they are not study specific, they provide pertinent CKD information that could motivate subjects to want to learn more about how to protect their kidneys. Study Patient information Sheets will be available for interested parties.

A total of 100 clusters of 1 or more people from familial or peers groups will be enrolled. The actual number of subjects will depend on the volume of clusters with more than 1 person. This would include approximately 1/3 of the Harps MTM subjects that have both DM and HTN.

Inclusion Criteria

- Adults (any gender)>18 years old
- Enrolled in Harp's MTM program
- Has Known CKD or 2 of the 3 conditions covered in MTM (DM, HTN and Heart Failure)
- Not on dialysis

Exclusion Criteria

- unable to read or speak English
- history of significant cognitive dysfunction unless qualified caregiver is the one being educated
- not personally independent or without any social support

Risks and Benefits

A risk to study participants is the potential for loss of confidentiality of study data.

Measures to protect the confidentiality of study data will be implemented as described in the Data Handling and Recordkeeping section below.

Title: Pragmatic Approach to Chronic Kidney Disease Education in the Delta V.6

PI: [name]

Potential benefits include the education received can motivate changes that can protect their kidney function, slow CKD progression and empower them to become more active in their health care.

Ongoing monitoring of international guidelines will be done to ensure education goals remain current.

Data Handling and Recordkeeping

All data received from Harps will be de-identified prior to being sent to UAMS. UAMS study tools will be de-identified. At randomization, the subject will receive a study number including: Harps site #, enrollment #, study arm #, subject initials, and # of people in cluster. In clusters with more than 1 person, the leader will be 1, the 2nd person will be 2, the 3rd 3. The cluster members initials will not be used, they will link to the leader.

Example the first cluster in the study consists of 2 people at site 3 lead by John Doe and randomized to study arm 2. The study number would be 3.1.2.JD.1 for the leader and 3.1.2.JD.2 for the 2nd person.

Data sent to UAMS Research Team. Data can be submitted in REDCap or on Paper.

After Visit 1	Intake Sheet including that includes demographics and medical history, Pre-Test, List of Meds	
After Final Visit	Data Collection Sheet 1, Post-test, Program Evaluation & List of Meds	

EOS: death, start of dialysis or transplantation.

Data will be stored in the UAMS Research office with access limited to study personnel only. UAMS-maintained computers and servers will be used to maintain databased information.

The Principal Investigator will carefully monitor study procedures to protect the safety of research subjects, the quality of the data and the integrity of the study.

At the conclusion of the study, the data will be maintained and later destroyed in accordance with UAMS policy which is for seven years after final reporting or publication of a project, or longer if required by a sponsor or regulation. Any data from subjects who opt out will not be kept for future use.

Multisite Research

Harps district director and research coordinator will be responsible for the education and oversite of each of their sites and not be responsible to UAMS IRB oversight. UAMS will supply the educational tools for both pharmacist, their staff and study subjects. This will include the CKD: What You Need to

Know workbook, slide sets, CKD action plan, Label reading exercise, Web-based resource list, data collection sheets, pre and post tests and program evaluation. UAMS staff will participate in the initial education of Harps staff and future education, as requested. UAMS will make the 10 points of CKD Care for Primary Care Providers (PCPs) available to both Harps staff and local PCPs, as requested.

Harps oversight staff and UAMS research staff will have monthly web-based or face to face meetings, with additional communication as needed.

Reporting requirements are the same for each site and outlined in the data section above. A central site may be selected by Harps when the sites are selected and serve as a model or mentoring site.

Data Analysis

Study arms will be compared by RRT choice using logistic regression that includes covariates found to differ between the groups. Results will be reported in terms of odds ratios and their 95% confidence intervals. Each group will be compared on the ability to choose a modality by the end of their 2nd or 3rd MTM visit, depending on their study arm and at the end of the study (June 2022) by comparing pre and post testing and program evaluation answers. To ensure balance in patient characteristics across clusters chi-square or Fisher's exact test, as appropriate, will be used to evaluate categorical measures, whereas two-sample t-test or Wilcoxon rank test, as appropriate, will be used for continuous measures.

The primary study aim is the ability of the participants to choose a dialysis modality by the end of their second or third visit, depending on their study arm. Descriptive statistics will be used to examine the trend in the patients' ability to choose a dialysis modality, level of interest in kidney transplant, the selection of a possible donor and having enough information to decide across the two assessment periods.

Home dialysis (HOD) is underutilized in management of End Stage Renal Disease (ESRD) and there is a near universal agreement amongst nephrologists and professional societies for improving its rates with a target of around 30-40% of the prevalent ESRD population. Patients, when provided with comprehensive early CKD education, have repeatedly indicated their preferences at similar rates (around 30-40%) for HOD. Despite these findings, the rates of HOD are on the decline. The ADH SE region's HOD rate for incident ESRD patients is less than 3%, AR rate is 11%, the national rate in 10% and the pilot study using the CKD: What you Need to Know rate was 44% for the 68 subjects needing to start RRT by the end of the study and an addition 3 % were able to get pre-emptive transplants.

It is likely that the lack of patient awareness and education play a critical role in the low incident HOD rates. The factors that contribute to this lack of patient awareness and education include the fact that comprehensive

education programs require time- and resource consuming processes, needs multidisciplinary expertise, and are only partially compensated by the current reimbursement standards in the nation. Hence, only limited medical universities and few nephrology practices provide these programs. With over 300,000 Arkansans unaware they have CKD and close to 50,000 more having CKD but little access to proper education, expanding the pool of clinicians and sites that can deliver comprehensive nephrology developed patient education to a larger patient population over a wider geographical area in a cost effective manner has the potential to improve patient outcomes and save health care dollars. It is estimated that HOD saves as much as \$19,000 per patient per year compared to in-center hemodialysis (). Demonstrating that non-nephrology clinicians can effectively educate and support these patients will provide models that other clinicians can use. Increased access to local CKD patient education can improve outcomes for minorities, especially in rural areas, who are less likely to receive most kinds of care including evidence-based practices, home dialysis or transplantation. Developing patient-centered approaches to care, such as this project, can reduce disparities.

Secondary outcomes will be compared in all clusters. Because randomization seldom results in samples that are balanced on all baseline characteristics, information on control variables relevant to choice of dialysis mode will be collected, including age, gender, baseline intent to start home based dialysis, whether currently being followed by a nephrologist, patient engagement measured by the percent of visits where CKD patient initiated discussion took place and self-reported and provider confirmed outcomes listed in study plan. Pharmacists and staff time will be compared between arms and linked to costs to support each intervention arm. Tests appropriate for the measure will be used when comparing baseline characteristics between the research arms.

The sample size was based on what was appropriate for what could be reasonably be accomplished in the time frame with the available funding. Power based on the primary aim was a secondary consideration. A population of 100 clusters could result in a much larger population of subjects depending on the size of the clusters. Utilizing clusters to essentially train peer educators and describe their training methods, as well as, the outcomes of each of their cluster members can inform future research involving CKD peer educator led CKD patient education programs.

Ethical Considerations

This study will be conducted in accordance with all applicable government regulations and University of Arkansas for Medical Sciences research policies and procedures. This protocol and any amendments will be submitted and approved by the UAMS Institutional Review Board (IRB) to conduct the study.

This study meets the criteria for exempt review and does not require formal consent of the subjects. However, a Patient Information Sheet explaining the study will be provided to interested parties. After discussion with Harp's pharmacist, verbal consent will be obtained and completion of the pre-test will be evidence of consent. UAMS will receive no HIPAA data on subjects. All data will be de-identified as outlined above and a HIPPA waiver has been requested.

Dissemination of Data

Results of this study may be used for presentations, posters, or publications. The publications will not contain any identifiable information that could be linked to a participant.

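### Specific Aims and Data Analysis describe different primary outcomes, the logistic regression event is not named, and an arm-dependent assessment visit contradicts the single Visit 3 post-test scheduled for all arms

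*Combined protocol and SAP*

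**What the plan says.** **Outcome.** Specific Aims sets the primary aim as the effectiveness of pharmacists and their staff as educators, "evaluating effectiveness through patient choice of RRT in each arm (e.g. home dialysis choice rate". Data Analysis states: "The primary study aim is the ability of the participants to choose a dialysis modality". The model sentence in the same section reads: "Study arms will be compared by RRT choice using logistic regression". It promises odds ratios with 95% confidence intervals but names no event, no reference category and no rule for undecided answers.

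**Timing.** Data Analysis places the primary assessment "by the end of their second or third visit, depending on their study arm". Its comparison of the groups on ability to choose uses the same arm-dependent timing and adds the end of the study, June 2022. Nothing says which arm is assessed at which visit, or which time point is primary.

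**Schedule.** Study Design and Procedures says: "Each arm will receive pre and post testing and health literacy evaluation". Its visit table has one testing row for all arms: pre-test at Visit 1, nothing at Visit 2, post-test at Visit 3, evaluation at the end of the study. All three arms in the table have a Visit 3. Data Handling and Recordkeeping has the post-test sent after the final visit and lists no Visit 2 test.

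**The concern.** The two sections can be read as asking different questions: which therapy a person picks, or whether the person can pick one at all. Education could move either without moving the other. If the event is not fixed, the same answers can support more than one primary odds ratio, and a reader cannot confirm from the plan that the reported one was chosen in advance.

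Timing adds a second ambiguity. If the arm-dependent sentence were followed, arms would be compared after different numbers of contacts and different lengths of time in the programme, so the arm effect would be mixed with time. The June 2022 comparison adds another possible headline result.

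**Working it through.** The plan gives no expected rate, effect size or power for the primary outcome, so there is no figure to reproduce. The check compares the sections and then sizes the difference in classification.

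**1. The same answer under each wording**

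| Post-test answer | Able to choose a dialysis modality (Data Analysis) | Home dialysis choice (example in Specific Aims) |
|---|---|---|
| Home dialysis | success | success |
| In-center hemodialysis | success | not a success |
| Transplant | not stated | not a success |
| Undecided | not stated; presumably not a success | not a success |

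The main disagreement is the in-center row. Transplant is a further gap: it falls within RRT but is not a dialysis modality.

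**2. Which event the regression models.** Data Analysis says the groups will be compared on ability to choose, which favours that event. Against this, the model sentence uses the broader RRT term, and the paragraph naming the primary aim attaches descriptive statistics to the trend in ability to choose. The control variables include baseline intent to start home-based dialysis. The plan gives home dialysis rates but no rate for ability to choose. The natural reading is therefore likely but is not written down.

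**3. Number classified differently**

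- From Data Analysis: educated patients "have repeatedly indicated their preferences at similar rates (around 30-40%) for HOD".
- Assumed: those rates apply to participants who can choose, and everyone else who can choose picks another dialysis modality.
- Share classified differently = 1 − home share: 1 − 0.40 = 60% to 1 − 0.30 = 70% of those able to choose.
- Assumed: 100 clusters in three equal arms with one person each, so 100/3 ≈ 33 per arm, of whom 20 to 33 can choose.
- Lower end: 20 − 0.40 × 20 = 20 − 8 = 12 people (12/33 = 36% of the arm).
- Upper end: 33 − 0.30 × 33 = 33 − 9.9 ≈ 23 people (23/33 = 70% of the arm).

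**4. Timing**

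| Source | Primary assessment |
|---|---|
| Data Analysis | Visit 2 or Visit 3, by arm; also June 2022 |
| Visit table | post-test at Visit 3, all arms; only the evaluation at end of study |
| Data Handling and Recordkeeping | post-test sent after the final visit |

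The table states: "Presumed monthly visits". Visit 2 is then about one month after Visit 1, and Visit 3 about two. Arm-dependent assessment would put arms about one month and one contact apart.

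**The case against.** The strongest reply is that Data Analysis does name a primary aim and does say the groups will be compared on it, while Specific Aims offers the home dialysis rate only as an example. Patient choice of RRT can also be read as making any choice. This has force. A reader might infer that the plan has no primary outcome, or that the event is wholly open until the data are seen. The documents do not support that: ability to choose is named as primary, and what is missing is agreement between sections and a named regression event.

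The pre-test, post-test and evaluation forms are not supplied and may make ability to choose a clear yes/no item. That would settle how answers are recorded. It would not settle which item the regression models, or the visit conflict.

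On timing, a reader might infer that the arms will in fact be measured at different visits and that the comparison is therefore confounded. That is not shown either, because no Visit 2 test is scheduled and a schedule-led conduct would test everyone at Visit 3.

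Nor does the reading schedule show that a Visit 2 assessment would miss the relevant teaching. The plan says "education arms subjects will be asked to read 1 chapter of the workbook weekly", and the dialysis and transplantation choices are in Chapter 3. At that pace Chapter 3 is reached before Visit 2, and Arm 1 discusses Chapters 1-4 at Visit 2. The control arm has no workbook, so chapter counts do not apply to it.

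**Conclusion.** The point holds as an inconsistency that should be repaired. The two sections word the primary outcome differently, the regression event is unnamed, and the assessment timing in Data Analysis contradicts the visit table and the data submission plan. June 2022 stands as a further, unranked time point.

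The classification difference is potentially large: 60-70% of those able to choose, or about 12 to 23 people in an arm of 33. This rests on applying preference rates from other educated patients to this trial, and on assumed values for arm size, cluster size and the number able to choose. The documents give no basis for estimating how far the odds ratio would move, so none is claimed. The timing difference, about one month and one contact, would arise only if the arm-dependent sentence were followed over the table.

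This is a pilot sized by feasibility and funding, with no success threshold. What is at stake is an interpretable primary result that can be shown to have been fixed in advance, not a pass/fail decision.

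**What to change.** 1. State one binary primary endpoint identically in Specific Aims and Data Analysis, and name it as the logistic regression event. Closest to the present Data Analysis text: able to choose a dialysis modality, yes/no, with undecided counted as no and the coding of a transplant answer stated.
2. Assess it at the Visit 3 post-test in all arms, and delete the wording that makes the visit depend on arm.
3. Label the June 2022 comparison secondary.
4. Report home dialysis choice as a secondary endpoint if the forms capture it. Baseline intent to start home-based dialysis is already planned as a control variable; whether the choice is also recorded at post-test must be checked on the forms. If the sponsor prefers home dialysis choice as primary, the roles can be swapped, provided both sections agree.

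The cost is a wording change in two sections. No new visit or test is needed, because the Visit 3 post-test is already scheduled. The downside is that the sponsor gives up the option to headline the other endpoint or the other time point.

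### Site pharmacists enrol clusters and also randomise them from a site schedule, and no step conceals the next allocation or fixes the cluster and pre-test first

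*Combined protocol and SAP*

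**What the plan says.** **Who does what.** Under Study Design and Procedures, Harps "pharmacists will screen patients in their MTM program and enroll them in familial or peer clusters consisting of 1 or more subjects" and then "randomize them into 1 of the 4 study arms using a site specific randomization schedule". The same section gives the teaching to pharmacists and their staff; Arm 1, for example, is a "case management model including pharmacist initiated discussion of workbook content and action plan reinforcement". The visit table shows different handouts and different pharmacist tasks by arm from Visit 1.

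**The schedule.** The only further detail, in the same section, is that subjects are randomised "using a site specific computer generated randomization schedule". No holder of the list, method of release or block structure is given.

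**The study number.** Data Handling and Recordkeeping states: "At randomization, the subject will receive a study number including: Harps site #, enrollment #, study arm #, subject initials". The sentence goes on to list cluster size as a further component. The worked example, a cluster already made up of two people, reads: "The study number would be 3.1.2.JD.1 for the leader and 3.1.2.JD.2 for the 2nd person".

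**The pre-test.** The visit table places it at Visit 1. Ethical Considerations says that "completion of the pre-test will be evidence of consent". Neither section places it before or after randomisation.

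**Adjustment.** Data Analysis plans a logistic regression with whichever covariates turn out unequal between groups, and names the intention at baseline to use home dialysis among the control variables.

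**The concern.** Pharmacists as a group screen, enrol, allocate and teach. Because the arms are open, a site knows its past allocations. If the enroller can also see or infer the next one, enrolment can be timed, a patient passed over, or a relative brought in according to the arm. Discretion is wide: clusters may have any number of members, and total subjects are left open. Arm 1 also asks much more of the pharmacist than the control arm, so allocation affects the allocator's own workload.

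The stake is the comparison of dialysis choice between arms. More motivated people could gather in one arm, and motivation is only partly captured by the listed covariates. If the pre-test is completed once the arm is known, participation itself and the baseline intention used for adjustment could also depend on the arm.

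**Working it through.** The plan states no figure on allocation concealment, so there is none to reproduce. The check has three parts.

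**1. The text, step by step**

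| Step | What is stated | What is not stated |
|---|---|---|
| Screening and enrolment | Harps pharmacists | – |
| Randomisation | Same pharmacists, site-specific schedule | Who holds or can see the schedule |
| Sequence | Computer generated | Blocked or simple; any central release or envelopes |
| Cluster roster and leader | Leader chosen by the cluster; cluster size listed as part of the study number | A rule fixing roster and leader before release |
| Pre-test and consent | Visit 1; pre-test is the evidence of consent | Order relative to randomisation |
| Study number | Issued at randomisation, with enrolment number and arm | Whether it is on the pre-test when the patient completes it |

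Computer generation describes how the sequence is made, not who sees it. The study number cannot reveal a subject's own arm beforehand, because it is issued at randomisation. It does leave a running record of arms at the site.

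**2. How predictable the next arm could be (illustration)**

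Assumptions: three arms, equal allocation, past allocations known, and a guesser who names the arm with most places left in the block. At each position the chance of being right is (largest number of places left in any arm) / (all places left), averaged over possible histories and then over positions.

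- Schedule visible: 100%.
- Simple randomisation: 1/3 = 33%; past allocations give no advantage.
- Blocks of 3: (1/3 + 1/2 + 1)/3 = 1.833/3 = 61%.
- Blocks of 6: (0.333 + 0.400 + 0.500 + 0.533 + 0.600 + 1)/6 = 3.367/6 = 56%.
- Blocks of 9: the same enumeration gives 53%.

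The section mentions four arms once but describes three. With four arms the figures are 25% under simple randomisation and 52%, 47% and 44% for blocks of 4, 8 and 12. The plan mentions no blocking, so simple randomisation is as consistent with the text as any block size.

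**3. What selection could do to the result (illustration)**

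Assumptions: no true effect; home dialysis chosen by 50% of motivated and 20% of other subjects; the motivated share averages 50% and differs by *s* between two arms.

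False difference = *s* × (50 − 20) points.

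| *s* | Rates in the two arms | False difference | Odds ratio |
|---|---|---|---|
| 10 points | 36.5% vs 33.5% | 3 points | 1.14 |
| 20 points | 38.0% vs 32.0% | 6 points | 1.30 |
| 30 points | 39.5% vs 30.5% | 9 points | 1.49 |

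With 100 clusters over three arms, about 33 each, a 10 to 30 point shift is roughly 3 to 10 clusters in an arm. The values of *s* are chosen, not derived from the guess rates in part 2.

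**The case against.** The strongest reply is that this is a risk inferred from silence. The documents do not say that the list is visible to the enroller, and a computer-generated simple sequence that is kept hidden would give no advantage. That limits the claim to an absent safeguard.

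A reader might infer four stronger things, none of which the text supports.

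- *That one individual does every step.* The plan speaks of pharmacists in the plural and also of staff. Clusters are family or peer groups that choose their own leader.
- *That members can be added after allocation.* The example uses the last field of the study number as a member index, but the list of components gives cluster size, and the example cluster already has two people. Late joining is neither shown nor excluded.
- *That the pre-test is completed with the arm known.* Its use as evidence of consent fits equally well with completion before allocation. The order is simply not stated.
- *That selection will occur, or that 3 to 9 points is an estimate of it.* Every input to that range is assumed.

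It is also fair to say that this is a pilot sized by feasibility. With 33 single-person clusters per arm and a 35% choice rate (both assumed), the 95% half-width for a difference is 1.96 × √(2 × 0.35 × 0.65 / 33) = 0.23, or about 23 points, well above the illustrated bias. That lessens urgency but does not excuse bias: imprecision is reported in the interval, whereas selection bias is not.

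What stands is that no section supplies concealment, and that adjusting for measured covariates would not remove selection on unmeasured motivation.

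**Conclusion.** The concern holds as a weakness of the stated procedure. The role that screens and enrols clusters also randomises them from a site schedule and shares in delivering open arms. Nothing described keeps the next allocation from the person enrolling, and no rule settles roster, leader or pre-test first. If the pre-test follows allocation, participation and baseline intention could depend on the arm; whether it does is not stated.

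The size cannot be derived from the documents. Predictability runs from chance level (simple randomisation, list hidden) to certainty (list visible), with assumed blocks in between. The possible bias is illustrative only. The change should be made because it is cheap and protects the primary comparison, not because selection has been demonstrated.

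**What to change.** - **Schedule.** UAMS holds it. The number of arms must be reconciled before it is generated.
- **Order.** The site first registers the cluster: roster, named leader, and consent and pre-test for each member on the roster. Only then is the arm released.
- **Release.** Use a REDCap allocation step, or numbered, sealed, opaque envelopes prepared by UAMS at paper sites. The REDCap step is a new set-up, since the plan uses REDCap only for submitting data.
- **Study number.** Issue it at registration without the arm digit. Keep a cluster and member identifier so that members still link to their leader, and store the arm as a separate field.
- **Late joiners.** Describe people who join after release, but leave them out of the comparative analysis.

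Cost: one set-up task, a changed identifier format, and a short wait before Visit 1 teaching. The wait may be longer for multi-person clusters, because every listed member's pre-test must be in first. No extra staff are needed.
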